Adherence to Methotrexate in Rheumatoid Arthritis: Effect of an Information Booklet on Methotrexate Levels

Methotrexate Adherence Project

Methotrexate Adherence Project

RESEARCH REFERENCE NUMBERS

PROTOCOL VERSION NUMBER 2 20th August 2018

Sponsor: Northumbria Healthcare NHS Foundation Trust

IRAS Number: 189766

CPMS 37811

TRIAL SUMMARY

Trial Title	Adherence to Methotrexate in Rheumatoid Arthritis: Effect of an Information Booklet on Methotrexate Levels	
Internal ref. no. (or short title)	Methotrexate Adherence Project	
Clinical Phase	IV	
Trial Design	Mixed Methods	
Trial Participants	Subjects with Rheumatoid Arthritis on a stable dose of Methotrexate	
Planned Sample Size	100 participants	
Treatment duration	3 – 6 months	
Follow up duration	none	
Planned Trial Period	18 months	
	Objectives	Outcome Measures
Primary	Does Education using an Information Booklet have an impact on Methotrexate Adherence and Disease Management	The responses of 100 patients with RA on Methotrexate to the Methotrexate Adherence Questionnaire and the Rheumatoid Arthritis Knowledge Questionnaire will be analysed qualitatively and quantitatively
Secondary	Do changes in Methotrexate Polyglutamate Assays detect Methotrexate Adherence	Methotrexate Polyglutamate Assays will be measured in venous blood samples of the study population

FUNDING AND SUPPORT IN KIND

FUNDER(S)	FINANCIAL AND NON FINANCIAL SUPPORT GIVEN
Chugai Pharmaceuticals Ltd UK	Financial support given
University of Newcastle Upon Tyne	Processing of blood samples
Northumbria Healthcare NHS Foundation Trust	Study Sponsor

[figure not shown]
KEY TRIAL CONTACTS

Chief Investigator	
[name]
 
Senior Research Nurse
 
Northumbria Healthcare NHS Foundation Trust
 
Co-Investigator:
 
[name]
 
Consultant Rheumatologist
 
Northumbria Healthcare NHS Foundation Trust

Trial Co-ordinator	
[name]
 
Senior Research Nurse
 
[contact]
 
[name]

Sponsor	
Northumbria Healthcare NHS Foundation Trust
 
North Tyneside General Hospital
 
Clinical Trials Office, [name]
 
[name]

Joint-sponsor(s)/co-sponsor(s)	N/A
Funder(s)	Chugai Pharmaceuticals Ltd UK
Clinical Trials Unit	N/A
Key Protocol Contributors	[name]
Statistician	N/A
Trials pharmacist	N/A
Committees	The INFLAME patient group, North Tyneside

LIST of CONTENTS

GENERAL INFORMATION	Page No.
TITLE PAGE	1
RESEARCH REFERENCE NUMBERS	2
TRIAL SUMMARY	3

1 BACKGROUND

The aim of this study is to explore any effect of the Rheumatoid Arthritis information booklet (Chugai/Roche 2014a) on the disease management and drug adherence of patients with Rheumatoid Arthritis (RA) taking Methotrexate. We also wish to explore the usefulness of red cell glutamate levels in determining Methotrexate Adherence levels.

Methotrexate is the default disease modifying drug (DMARD) for treatment of RA. It is a drug which has a delayed onset of action and where the majority of patients, even those continuing on treatment, have side effects that they tolerate in order to stay on the drug (Walker et al 2014). Poor drug adherence can give the impression that the therapy has failed which could lead to an economic impact (O’Niell 2011).

The definition of adherence is not straightforward, Haynes et al (2002), describe it as “the extent to which a person’s behaviour coincides with medical or health advice” or Kelly (1995) who suggests “following medical advice sufficiently to achieve the therapeutic goal’. We think that patients can be divided into “Non Adherence”: those patients who stop their prescriptions completely and do not pick up repeat prescriptions; Partial adherence, divided into those who partially adhere but whose disease is under good control; and those who miss medications often enough for their disease not to be under good control.

The reasons for incomplete adherence are only partly understood. They may relate to the tolerance problems (Hill 2005). Some patients find adhering to medication regimes a chore (Duerden 2013). Understanding why they are taking the drugs has been shown to improve adherence (Hill 2005). Jackson (2014) has divided the reasons into Capability; Opportunity and Motivation.

A World Health Organisation survey of a long term drug use indicates that as many as 40% of patients do not take their prescriptions as intended (2003). Patients have admitted to us of not always taking the Methotrexate and to taking a “Methotrexate holiday” when they can’t face taking it (Walker et al 2014). They are often reluctant to divulge this to the healthcare staff they see. There are many reasons for this ranging from embarrassment, not wanting to “upset” their health care provider to fearing that their drugs may be stopped.

Educating patients about the drug and why they are taking it has been shown to improve adherence (Quinlan 2009) “The finding that health knowledge, especially medication knowledge, is influenced by health literacy, age, income and education”. Chugai/Roche have recently produced a booklet for people who have Rheumatoid Arthritis (Chugai/Roche 2014a). This has been designed with psychology input to prompt the patients to think about and then assess using a scale from 0 – 10 how their treatment suits them across 7 domains. These domains reflect drug use, efficacy, side effects and drug concerns. A low score in a domain prompts the user to turn to a certain section in the booklet for more information. A pilot study of the booklet has shown it to be well received and useful to patients (Chugai/Roche 2014b).

Measuring adherence is also a problem as patients may not be entirely open about how they take their drugs. Questionnaires have been used, but we suspect from talking to patients and health care professionals, that, who delivers the questionnaire and how it is delivered may make a difference to responses. Methotrexate is quickly cleared from the blood, but metabolites known as polyglutamates collect in the red cells (RC-polyglutamates) and give a longer look at drug taking. We plan to measure these for comparison with the Methotrexate dose and the adherence data.

Benefits of the Study to the NHS

The World Health Organisation (2003) reports that around 40% of patients do not take medication as prescribed; this could lead to poor disease management, waste, prescription of more expensive drugs and increased in-patient attendance. All of these factors could potentially have a financial burden on the NHS. The NHS FIVE Year Forward View (NHS 2014) describes “empowering patients”, encouraging patients to manage their own health, make informed treatment choices and provide opportunities for self-management education (NHS 2014:12). We want to understand how patients self-manage their own treatment, what impact this has on their disease and how far this could impact on the financial burden of the NHS. We want to be able to recognise and understand those situations where patients are self-managing well and when they are not. We also want to understand if education around their disease and treatment could make a positive impact on drug adherence and therefore disease management which would contribute to the financial plan of the NHS Five Year Forward View (NHS 2014:36).

This study has been given financial support from Chugai Pharmaceuticals Ltd UK. It underwent formal internal review by Chugai Clinical Support Group and Clinical Finance Group. A CPU Investigator Initiated Study Agreement is in place between the Sponsor, Northumbria Healthcare NHS Foundation Trust and Chugai Pharmaceuticals Ltd, UK.

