3.3 Outcome measures

3.3.1 Primary endpoint/outcome

The primary outcome measure is the responses to the Methotrexate Adherence and the Rheumatoid Arthritis Knowledge questionnaires. Subjects will be randomised 50:50 to receive the Rheumatoid Arthritis information booklet. Those participants who do not receive the booklet at randomisation will receive it 3 – 6 months later when the participant returns for their routine Methotrexate blood monitoring appointment. The aim of this is to determine whether the intervention of the Rheumatoid

Arthritis information booklet has an impact on patient Methotrexate management. All patients will be given the Methotrexate Adherence questionnaire and the RA Questionnaire at screening and again 3 – 6 months later.

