7 TRIAL PROCEDURES

7.1 Recruitment

Potential study participants will be recruited at their routine Methotrexate blood monitoring clinic having been identified by the clinical team first. Potential participants will be given a Patient Information Leaflet describing the study, which will describe “Methotrexate Management” rather than “Methotrexate Adherence”. Using the word “Adherence” may affect the way the participants take their medication in order to be compliant with Methotrexate whilst on the study and we wish to avoid that bias. A diagnosis of Rheumatoid Arthritis will be determined by consulting the patients’ notes with their consent. All data collected on the study will be anonymised and each participant will be given a unique study number for identification and safety.

The following data will be collected:

- age
- gender
- ethnicity
- Dose of Methotrexate
- How long on this dose
- Route of administration

- Day of the week Methotrexate is taken
- Other concomitant medication

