7.4 Baseline Data

The following data will be collected at baseline:

- Age in years
- Gender
- Ethnic Origin
- Dose of Methotrexate the subject is currently taking
- Route of Administration
- Date the subject was first prescribed Methotrexate
- Medical history
- Concomitant Medication

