7.5 Study Assessments

- Baseline and follow up Methotrexate Adherence questionnaire
- Baseline and follow up Rheumatoid Arthritis knowledge questionnaire
- Two blood test for RC-MTX polyglutamate levels

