9 DATA HANDLING

9.1 Data collection tools and source document identification

Source Data

ICH E6 section 1.51, defines source data as "All information in original records and certified copies of original records or clinical findings, observations, or other activities in a clinical trial necessary for the reconstruction and evaluation of the trial. Source data are contained in source documents (original records or certified copies)."

Source Documents

ICH E6 1.52, defines source documents as "Original documents, data and records (e.g., hospital records, clinical and office charts, laboratory notes, memoranda, subjects' diaries of evaluation checklists, pharmacy dispensing records, recorded data from automated instruments, copies or transcriptions certified after verification as being accurate and complete, microfiches, photographic negatives, microfilm or magnetic media, x-rays, subject files, and records kept at the pharmacy, at the laboratories, and at medico-technical departments involved in the clinical trial)."

Case report forms

The lead study nurse and the PI will ensure that:

- adequate collection of data has been performed
- proper paper trails will be kept to demonstrate the validity of the trial (both during and after the trial)
- only the data required by the protocol are captured in the CRF (using the CRF to capture secondary data not required for the study may be a criminal breach of the Data Protection

Act, makes the CRF unnecessarily complicated, and can make it more difficult to extract the primary data for analysis)

10 Data handling and record keeping

- Data will be entered onto paper CRFs and patients' hospital notes. This data will be checked by the lead study nurse and the CI.
- All data will be stored in study files which are located in a locked office in The Clinical Trials Office at North Tyneside Hospital. No identifiable data will leave Trust facilities.
- No identifiable data will be transferred out of Northumbria Healthcare NHS Foundation Trust. No identifiable data will be recorded on blood samples only the subject's unique study number.
- All study participants will be allocated a unique study number as and when they give informed consent and study enrolment. This will be carried out by the research team.
- The lead study nurse is responsible for data entry and quality.
- Study personnel are responsible for data analysis.

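### Of four influences on knowledge that the Background cites, only age is recorded; one education item, plus adjustment for baseline score and age, would add modest precision and describe drop-out

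*Protocol*

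**What the plan says.** Protocol section 1 (Background) supports the educational rationale with a cited finding that "health knowledge, especially medication knowledge, is influenced by health literacy, age, income and education". Section 3.3.1 then states: "The primary outcome measure is the responses to the Methotrexate Adherence and the Rheumatoid Arthritis Knowledge questionnaires". Knowledge is therefore a primary outcome, and the protocol itself cites four influences on it.

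Two lists fix what is recorded about each participant.

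- Section 7.1 ("The following data will be collected") has age, gender, ethnicity, methotrexate dose, time on that dose, route, day of the week taken, and other medication.
- Section 7.4 ("The following data will be collected at baseline") has age, gender, ethnic origin, dose, route, date of first prescription, medical history and concomitant medication.

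Neither list has education, health literacy or income. Section 9.1 adds that "only the data required by the protocol are captured in the CRF".

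Three other provisions bear on the point.

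- The knowledge score is taken before and after: "All patients will be given the Methotrexate Adherence questionnaire and the RA Questionnaire at screening and again 3 – 6 months later". Section 7.5 agrees: "Baseline and follow up Rheumatoid Arthritis knowledge questionnaire".
- Allocation is random: "Subjects will be randomised 50:50 to receive the Rheumatoid Arthritis information booklet".
- Section 8.3 plans a mainly descriptive analysis, and the inferential tests it gives as examples (t-test, Mann-Whitney, Wilcoxon, chi-squared) are unadjusted.

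**The concern.** The intervention is a booklet that patients read by themselves. Education and literacy could plausibly affect both what a patient knows at the start and how much is gained from reading. The baseline score picks up the first. It does not pick up a difference in gain, nor a difference in who comes back.

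The second matters here because section 8.2 counts drop-out and missing questionnaire data among the key outcomes of this pilot and allows up to 30% loss. As written, the pilot could not say whether those lost differ in education from those who stay, and that would be useful when planning retention, covariates and strata for the definitive trial.

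This is not a matter that can wait for an analysis plan. Such a plan can choose covariates, but only from data that were collected, and participants who have dropped out cannot reliably be asked afterwards.

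**Working it through.** **Inputs from the protocol.** Minimum 35 per group, drop-out at most 30%, 50 recruited per group (section 8.2); 1:1 allocation (3.3.1); blocked schedule with no stratification factor named (7.3).

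**Inputs assumed, because the protocol gives none.** Share with low educational attainment 40%; difference in knowledge between low and high education 0.8 SD; correlation of education with follow-up knowledge r = 0.4, with baseline knowledge s = 0.2 to 0.4; correlation of baseline with follow-up knowledge ρ = 0.4 to 0.6. The first three agree with one another: 0.8 × √(0.4 × 0.6) = 0.39.

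**1. The plan's own figure.** 35 / (1 − 0.30) = 50 per group. It reproduces, and nothing below changes it.

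**2. Size of chance imbalance.** SD of the between-arm difference in the share with low education = √(2 × 0.4 × 0.6 / n).

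| | n = 50 per arm | n = 35 per arm |
|---|---|---|
| SD of difference | 0.098 | 0.117 |
| 95% range (× 1.96) | ±19 points | ±23 points |
| Exact binomial chance of a gap of 15 points or more | 12.5% | 17.9% |

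A gap of that size is possible but not likely.

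**3. What such a gap does to the knowledge contrast.**

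- Unadjusted: 0.8 × 0.15 = 0.12 SD, up to 0.8 × 0.20 = 0.16 SD.
- The 95% half-width for the unadjusted contrast at 35 per arm is 1.96 × √(2/35) = 0.47 SD, so the shift is about a quarter to a third of it.
- After adjustment for the baseline score, the fraction of the shift that remains is (r − ρs)/r. At ρ = 0.4 this is 80% (s = 0.2) or 60% (s = 0.4). At ρ = 0.6 it is 70% or 40%.
- The remaining shift is then between 0.12 × 0.40 = 0.05 SD and 0.16 × 0.80 = 0.13 SD.
- If education correlates equally with both scores and ρ is 0.5 to 0.8, the fraction is 1 − ρ, that is 20 to 50%.

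**4. Precision from adjustment.** Residual variance is 1 − ρ² with the baseline score alone. With education added it is 1 − (ρ² + r² − 2ρrs)/(1 − s²).

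| ρ | s | Baseline score only | With education | Further variance removed | Interval narrower by |
|---|---|---|---|---|---|
| 0.4 | 0.2 | 0.840 | 0.733 | 12.7% | 6.6% |
| 0.4 | 0.4 | 0.840 | 0.771 | 8.2% | 4.2% |
| 0.6 | 0.2 | 0.640 | 0.558 | 12.8% | 6.6% |
| 0.6 | 0.4 | 0.640 | 0.610 | 4.8% | 2.4% |

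On a half-width of at most 0.47 SD, education therefore saves about 0.03 SD at most. The baseline score alone narrows the unadjusted interval by 1 − √0.84 = 8% to 1 − √0.64 = 20%. Most of the available gain comes from data the protocol already collects.

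**The case against.** The strongest reply is that the protocol contradicts nothing. A background citation does not oblige a trial to measure everything it mentions, and a short baseline list is a legitimate choice in a pilot. Section 6.2 already excludes people who cannot read English, the booklet or the questionnaires, which removes the bottom of the literacy range. With at most about 30 drop-outs in total (30% of 100), any description of loss by education would be imprecise. The CRF limit in section 9.1 is routine data-minimisation wording and does not prevent an amendment. Most of this stands, and it is why the point is one of modest improvement. It does not supply the missing variable: the reading exclusions shorten the literacy range without measuring what remains, and an imprecise description of drop-out is still more than none.

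A reader might infer that imbalance on the drivers of a primary outcome can be neither seen nor adjusted for. The documents do not support that. Age is one of the four and is on both lists. The knowledge questionnaire is completed by both arms at the start (3.3.1 and 7.5), so imbalance that shows in starting knowledge is visible and adjustable. A reader might also infer bias, or that material imbalance is likely. Under randomisation the imbalance is chance that the standard error already covers, and the chance of a 15-point gap is only about 12 to 18% under the assumed prevalence.

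**Conclusion.** The point holds as a design gap of modest weight. The protocol cites four influences on a primary outcome, records one of them, and confines the CRF to what it lists. Neither the sample size nor the validity of the randomised comparison is affected.

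The loss is of two kinds. The first is precision: about 2 to 7% of interval width beyond the baseline score, which depends wholly on the assumed correlations. The second is description: who was recruited, who was lost, and whether response to a written booklet varies with education. The second needs no assumed correlation and is the better reason to act, since drop-out is a stated outcome of the pilot.

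One caveat concerns the baseline score on which the milder reading rests. The schedule in Appendix 4 shows no marks against the RA Knowledge Questionnaire in the text available. That may be a matter of layout, but the schedule should be checked against 3.3.1 and 7.5.

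**What to change.** 1. Add one item to the lists in 7.1 and 7.4, asked of everyone before randomisation: highest educational qualification, or age on leaving full-time education. It is a practical proxy; health literacy and income would stay unmeasured, and the report should say so.
2. Tabulate it by arm and by completion status.
3. In section 8.3, in place of reliance on the unadjusted example tests, state that the between-arm comparisons of knowledge and of adherence adjust for the baseline score of the same questionnaire and for age, with education as a further covariate. The baseline score and age need no new data and could be specified even if the education item were declined.
4. Confirm in Appendix 4 that the knowledge questionnaire is given at both time points.

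The cost is one question, one CRF line, a short amendment, one more item of personal data per participant, and one or two degrees of freedom for education. No extra visits, staff or patients are needed. For anyone randomised before the amendment, education would be missing or asked late, and the table should show how many.

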2 RATIONALE

We are interested to explore whether this booklet, used by patients, would improve self-management of disease and adherence to Methotrexate. Our primary outcome measures will be the responses to a Methotrexate Adherence questionnaire and a Rheumatoid Arthritis Knowledge questionnaire. We will also have the opportunity to compare the Methotrexate Adherence questionnaire with an objective blood test measuring the RC-MTX polyglutamate blood levels to the prescribed dose of Methotrexate.

2.1 Assessment and management of risk

This trial is categorised as:

- Type A = No higher than the risk of standard medical care

See Appendix 1

3 OBJECTIVES AND OUTCOME MEASURES/ENDPOINTS

3.1 Primary objective

The primary objective of this project is to determine if a Rheumatoid Arthritis information booklet increases understanding of Rheumatoid Arthritis in patients with this disease and leads to better disease management through drug adherence.

3.2 Secondary objectives

The secondary objective is to measure blood Methotrexate levels in order to detect drug compliance.

3.3 Outcome measures

3.3.1 Primary endpoint/outcome

The primary outcome measure is the responses to the Methotrexate Adherence and the Rheumatoid Arthritis Knowledge questionnaires. Subjects will be randomised 50:50 to receive the Rheumatoid Arthritis information booklet. Those participants who do not receive the booklet at randomisation will receive it 3 – 6 months later when the participant returns for their routine Methotrexate blood monitoring appointment. The aim of this is to determine whether the intervention of the Rheumatoid

Arthritis information booklet has an impact on patient Methotrexate management. All patients will be given the Methotrexate Adherence questionnaire and the RA Questionnaire at screening and again 3 – 6 months later.

3.3.2 Secondary endpoints/outcomes

The secondary outcome measure is the measurement of RC-MTX polyglutamate levels in a venous blood sample at two timepoints from all study patients to detect if Methotrexate Adherence correlates with RC-MTX polyglutamate levels.

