6 ELIGIBILITY CRITERIA

6.1 Inclusion criteria

- Subjects capable of giving informed consent in English
- Male or female
- Over the age of 18 years

- Diagnosis of Rheumatoid Arthritis
- On a stable dose of Methotrexate for at least 3 months

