7.6 Withdrawal criteria

Participants will be withdrawn from the study if:

- They withdraw consent
- Stop taking Methotrexate or change their stable dose
- Are unable to return to clinic for their routine 3 – 6 month blood monitoring appointment
- In the PI's opinion it is in the best interests of the participant to withdraw from the study

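### The secondary endpoint in section 3.3.2 omits the comparison with prescribed dose that the Background and Rationale announce, so differences in dose and route between patients can weaken or bias the correlation

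*Protocol*

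**What the plan says.** The protocol describes the use of polyglutamate levels in several places, and the descriptions differ.

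- **Section 3.3.2** gives the secondary outcome as levels at two time points in all patients, "to detect if Methotrexate Adherence correlates with RC-MTX polyglutamate levels". Neither dose nor route is mentioned.
- **Trial Summary**, secondary objective: "Do changes in Methotrexate Polyglutamate Assays detect Methotrexate Adherence". This is a question about change, again without dose.
- **Section 1 (Background)**: "We plan to measure these for comparison with the Methotrexate dose and the adherence data".
- **Section 2 (Rationale)** speaks of comparing the questionnaire with a blood test "measuring the RC-MTX polyglutamate blood levels to the prescribed dose of Methotrexate".
- **Section 6.1** admits patients "On a stable dose of Methotrexate for at least 3 months". It sets no particular dose, dose range or route.
- **Section 7.6** withdraws patients who "Stop taking Methotrexate or change their stable dose". Section 4 lets some patients with an interruption stay in if they are back on their original dose for long enough before the second sample.
- **Sections 7.1 and 7.4** collect both variables: "Dose of Methotrexate the subject is currently taking" and "Route of administration".
- **Section 8.2** plans to collect change in adherence and change in polyglutamate level from baseline to follow-up.

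**The concern.** A polyglutamate level reflects how much methotrexate is prescribed and by which route, as well as how much of it is taken. Two patients who adhere equally well on different doses can be expected to differ in level. If levels are correlated with the questionnaire without regard to dose, that difference counts as noise. If prescribed dose also happens to be related to adherence, it becomes confounding.

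The Background and Rationale show that the authors meant to read levels against dose. The endpoint definition is what an analyst will follow, and it leaves dose out. An analysis faithful to section 3.3.2 could therefore report a weak correlation and suggest that the assay does not track adherence, when the weakness comes from a mixture of doses. It could also report a correlation that arises only through dose. Section 8.2 intends the polyglutamate data to help plan a definitive trial, so either error could carry forward.

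**Working it through.** **The plan's own figure.** The protocol states no number for the correlation endpoint. Its only related figure is the recruitment target in section 8.2: 35 evaluable per group with 30% drop-out gives 35 / (1 − 0.30) = 50 per group, 100 in total. This reproduces. It leaves 2 × 35 = 70 patients at follow-up in the worst case planned for, and up to 100 with baseline samples.

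**Inputs from the protocol.** n = 70 or 100; two-sided 5% significance (section 8.3).

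**Inputs assumed, because the protocol gives none.**

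- ρ: correlation of adherence with level after adjustment for dose, taken as 0.30 or 0.40.
- v: share of the variance in level explained by dose, 0.1 to 0.5.
- c: correlation of adherence with dose, −0.3 to +0.3.

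**Step 1: dose unrelated to adherence (c = 0).** The unadjusted correlation is r = ρ × √(1 − v). For ρ = 0.30 and v = 0.3, r = 0.30 × √0.7 = 0.251. Power is Φ(atanh(r) × √(n − 3 − k) − 1.96), where k is the number of adjusting covariates: 0 unadjusted, 1 with dose.

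| ρ | v | unadjusted r | power, n = 70: unadjusted / adjusted | power, n = 100: unadjusted / adjusted |
|---|---|---|---|---|
| 0.30 | 0.1 | 0.285 | 66.8% / 71.0% | 82.2% / 85.8% |
| 0.30 | 0.3 | 0.251 | 55.5% / 71.0% | 71.4% / 85.8% |
| 0.30 | 0.5 | 0.212 | 42.2% / 71.0% | 56.4% / 85.8% |
| 0.40 | 0.1 | 0.379 | 90.5% / 93.1% | 97.6% / 98.6% |
| 0.40 | 0.3 | 0.335 | 81.3% / 93.1% | 92.9% / 98.6% |
| 0.40 | 0.5 | 0.283 | 66.3% / 93.1% | 81.7% / 98.6% |

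**Step 2: dose related to adherence (c ≠ 0).** The unadjusted correlation becomes r = ρ × √((1 − v)(1 − c²)) + c × √v. With v = 0.3 and c = ±0.3, the second term is ±0.3 × √0.3 = ±0.164.

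- If ρ = 0, then r = ±0.164: an apparent relation where there is none at a given dose.
- If ρ = 0.30, the first term is 0.30 × √(0.7 × 0.91) = 0.239, so r runs from 0.075 (c = −0.3) to 0.404 (c = +0.3).
- Over v = 0.1 to 0.5 with ρ = 0.30, r runs from 0.177 down to −0.010 when c = −0.3, and from 0.366 up to 0.414 when c = +0.3.

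**Step 3: price of adjusting when it was not needed.** If v = 0 and c = 0, power at ρ = 0.30 and n = 70 is 71.7% with no covariate, 71.0% with one and 70.4% with two (dose and route).

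**Step 4: change within patients.** A patient who completes under sections 6.1 and 7.6 has the same prescribed dose at both samples. If level is roughly proportional to dose, the dose factor cancels from the change in log level. The problem is therefore mainly one of comparison between patients. The change data planned in section 8.2 would largely escape it, and they are also what the Trial Summary question calls for.

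**The case against.** Four objections carry weight.

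*The protocol does not ignore dose.* A reader of section 3.3.2 alone might infer that it does. The documents do not support this: the Background and the Rationale both announce a comparison with dose, and dose and route are recorded. Only route is absent from every stated comparison. What stands is narrower: the endpoint definition does not carry forward what those sections announce.

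*Section 3.3.2 names no estimator.* It says that adherence correlates with levels and does not say that the levels are unadjusted. Covariate adjustment is often left to an analysis plan, which is not shown here. Nor do the tests in section 8.3 settle the matter: they are examples, under a heading about the primary outcome, and include no correlation. This is fair. The point therefore rests on disagreement between sections about what is to be compared, not on a missing model. An analysis plan written to section 3.3.2 could use the unadjusted correlation and be faithful to it.

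*Change is already planned.* It might be inferred that the Trial Summary question about change is left without data. Section 8.2 collects change in both level and adherence, so only the link between the two remains to be stated. Equally, two samples per patient might suggest that they will be pooled as if independent. No section says so.

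*The numbers are assumed.* Every correlation and variance share above is an assumption, and 70 is the worst-case follow-up number. If dose explains little of the variance and is unrelated to adherence, the loss is small. This stands in full, and the figures show direction and plausible range only.

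**Conclusion.** The point holds as a mismatch with a practical consequence. Section 3.3.2 words the secondary endpoint as a plain correlation between adherence and level, the Background and Rationale say that levels are to be read against dose, and eligibility lets dose and route differ between patients. Followed as worded, the endpoint can give an attenuated correlation, or one biased in either direction if dose and adherence are related.

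The size cannot be derived from the protocol. Under the assumptions above, attenuation alone takes an adjusted correlation of 0.30 down to between 0.285 and 0.212. A dose–adherence correlation of ±0.3, with 30% of the variance due to dose, moves it to between 0.075 and 0.404. Importance is minor to moderate: the endpoint is secondary, the study is a pilot analysed mostly descriptively, and the sample size does not rest on this correlation.

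**What to change.** - Reword section 3.3.2 so that the endpoint is the association between adherence score and (log) polyglutamate level, adjusted for prescribed dose and route, by partial correlation or regression. If both time points enter one analysis, allow for two samples per patient, for example with a patient effect.
- Add the within-patient association of change in log level with change in adherence score, using the change data already planned in section 8.2. This answers the Trial Summary question.
- Report the unadjusted correlation as descriptive only.
- Align the Trial Summary and sections 1, 2 and 3.3.2 so that they state the same comparison.

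The cost is wording, a little more analysis work and one or two degrees of freedom, which is about one percentage point of power in the illustration when adjustment turns out to be unnecessary. No new data are needed.
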